2.0 STUDY DESIGN, AIMS AND OUTCOME MEASURES

The randomized, double-blind, sham-controlled, cross-over study will involve three sessions. The first session will involve a clinical interview, questionnaires, and EEG recording during a computerized task. The second and third sessions will involve tACS brain stimulation (or placebo stimulation) during a computerized task and EEG recording. Participant's psychiatric phenotypes and functioning will be dimensionally characterized. Affective cognitive control in bipolar disorder will be assessed using the Emotion Go-NoGo Task.

Aim #1: Evaluate the feasibility and acceptance of tACS among bipolar patients. Neuromodulation studies typically use dropout rate and reported adverse events as measures of acceptability and tolerability, respectively¹⁰. We will compare the percentage of participants requesting to discontinue the session and the severity of side effects reported following the tACS vs. sham procedure using Bayes factors (BF).

Intervention: One-session tACS

Primary outcome measure 1: Severity of side effects reported at end of stimulation session. This is calculated by summing the severity score of items (0-4) that are rated by the participant as related to stimulation (ratings of 3=probable or 4=definite) on the Stimulation Side Effects Questionnaire. **Primary outcome measure 2**: Withdrawal during or after the stimulation session.

Aim #2: Estimate the preliminary effects of personalized tACS on theta-gamma phase-amplitude coupling (PAC) and cognitive control behavior in BD.

Intervention: One-session tACS

Primary outcome measure 3: Accuracy signal detection theory metric sensitivity (d') derived from the behavioral responses to Go and NoGo trials on the cognitive control task.

Primary outcome measure 4: Accuracy signal detection theory metric response bias (β) derived from the behavioral responses to Go and NoGo trials on the cognitive control task.

Primary outcome measure 5: Reaction time (millisecond) of Go trials on the cognitive control task. **Primary outcome measure 6**: Theta-gamma PAC (Kullback-Leibler Modulation Index) during the rest EEG blocks interleaved between stimulation blocks.

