Flanker Task. After completing the Emotion Go-NoGo task, participants will perform a separate cognitive control task (i.e., Flanker task; described below). Accuracy and reaction time will be used to index cognitive control behavior as outcome measures. EEG recorded during the Flanker task will be used to assess neurological indicators of attention control. Participants will then be 50-50 randomized to receive either the Sham treatment first or tACS treatment first at Session 2.

7) Randomization. Subjects will be randomized on a 50-50 basis to receive active vs. sham stimulation. If participants are randomized to the active group at Session 2, they will go to the sham group at Session 3, and vice versa. The participant will not be told which group they were randomized to. The randomization schedule will ensure an equal distribution across the group. Randomization lists

will be generated by random condition generator and will be programmed into the computer that controls the tACS device by the postdoc fellow or PI.

Sessions 2 and 3: Sham vs. Active tACS Session (~2-3 hours)

These sessions will occur at the University of Michigan Rachel Upjohn Building. Participants will undergo two sessions, separated by ~ 1 week. Procedures will be identical for each session.

- 1) *Pre-Visit Preparations*. Research staff will contact the participant to remind them about the study visit and to ask if they have had any medication changes since their last visit. If yes, the participant will be re-scheduled for an appointment time in which the criteria for a stable dose of at least two weeks has been achieved. Additionally, participants will also be asked if they have had any recreational drug use since their last study visit. If yes, the participant will have to be re-scheduled 30 days out.
- 2) *Arrival on scheduled session day*. Participants will arrive at the Rachel Upjohn Building where they will be greeted by a member of research staff and escorted to the treatment room. Pregnancy urine test will be given if participant opted out of signing the Pregnancy Attestation Form.
- 3) *Clinician Administered Assessments*. In-person clinical assessments will be completed by a trained member of staff. All study clinicians are blinded to the treatment arm.

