Pleasant vs Neutral), and a grand total of 600 trials. Performance feedback will be provided and the stimuli presentation time will be adjusted based on performance after each block (e.g., if performance is above 90%, a 40ms shorter presentation time will be used in the next block) to ensure adequate number of errors and consistency in performance across participants within each part. Actual presentation and interval time may differ slightly in implementation from that described above. Estimated to take ~40 minutes. This task is designed to assess error and response monitoring within emotional contexts, which has been shown to be different from monitoring in other contexts, such as emotionally neutral context using arrows. Accuracy and reaction time will be used to index cognitive control behavior as outcome measures. EEG recorded during the Emotional Flanker task will be used to assess neurological indicators of attention control. [*Note: the timing and trial parameters of the actual task may be modified slightly depending on initial testing results. In order to reduce subject burden, experimenters may shorten the task and drop the display of pictures (neutral and valenced), using simple arrow cues instead to indicate a right or left button press].

Follow-up Phone Call (~ 5-10 min)

Approximately 4 weeks (+/- \sim 7 days) following the completion of Session 3, research staff will call to administer the Stimulation Side Effect Questionnaire as a final safety check and evaluate for any other possible side effects.

Stopping Rules

If a participant reports intolerable discomfort during the tACS procedure, the session will be discontinued. Immediately after each stimulation session ends, participants will complete a tACS side effects questionnaire. A study team member will review the responses and will immediately consult the PI if a participant reports a high (3) to very high (4) rating for any of the side effects rated to be related to the stimulation (4=probable or 5=definite). Subjects may also be withdrawn by the investigator when continued participation would present an unacceptable risk (e.g., worsening symptoms, suicidal thoughts, etc.).

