7.0 STATISTICAL CONSIDERATIONS

Aim 1 - Acceptability and Tolerability. Neuromodulation studies typically use dropout rate and reported adverse events as measures of acceptability and tolerability, respectively.¹² We will compare the percentage of participants requesting to discontinue the session and the severity of side effects reported following the tACS vs. sham procedure using Bayes factors (BF).

Aim 2 - tACS Effects on Neural Synchrony and Cognitive Control Behavior. EEG data preprocessing and spectral analyses will be conducted using custom MATLAB scripts and EEGLAB following the general methods described in **PI [name]**'s published work.⁷ Briefly, data will be downsampled to 500 Hz, filtered (0.1 – 100 Hz), re-referenced to common average, segmented into short epochs (for task data, -400 to 1800 ms time-locked to onset of stimuli; for rest data, 2 s epochs), applied independent component analysis to reject non-neural artifacts, baseline adjusted, followed by automatic artifact rejection of epochs containing voltage exceeding ±100 μ V. Data will be mirrored on both ends to minimize edge artifacts, applied Morlet wavelet convolution to extract power of different frequencies from 2 to 60 Hz. Theta-gamma PAC will be computed using the Kullback-Leibler Modulation Index (KLMI)⁸ implemented in the PAC Tools plugin for EEGLAB.⁹ Neural synchrony (theta-gamma PAC) during the rest EEG blocks and cognitive control performance (sensitivity d', response bias β , and reaction time on the Emotion Go-NoGo task) will be analyzed in separate repeated-measures ANCOVAs, with stimulation (tACS, sham) as within-subjects factor.

Potential Problems & Alternative Strategies

Participants Dropout. The study design entails each participant completing all 3 sessions. Our experience of conducting multiple-session neuromodulation studies suggests that average dropout rate for each subsequent session is 10-15%. We will enroll 30 participants to ensure that at least 20 participants will complete the study even with an overall dropout of 30%.

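### The Aim 1 analysis counts requests to discontinue a session, so it leaves out the post-session withdrawals that primary outcome 2 includes; how those should be attributed and compared is undefined

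*Combined protocol and SAP*

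**What the plan says.** Section 2.0 lists primary outcome 2 as "Withdrawal during or after the stimulation session". It gives no time limit for the post-session part, no rule for assigning a withdrawal to active or sham, and no denominator.

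The analysis is described differently. Section 7.0 (Aim 1) states: "We will compare the percentage of participants requesting to discontinue the session", with tACS set against sham by a Bayes factor. Section 2.0 carries the same sentence just above the outcome definition, and the synopsis has an equivalent one. None says whether sessions are pooled or paired, which participants are included, or what model and prior the Bayes factor uses. Sections 2.0 and 7.0 both introduce this analysis by saying that the field measures acceptability by dropout rate.

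On design, Section 5.2 states: "If participants are randomized to the active group at Session 2, they will go to the sham group at Session 3, and vice versa". It adds: "Participants will undergo two sessions, separated by ~ 1 week". In both sessions a Flanker task follows stimulation and the side effects questionnaire. Once Session 3 is over, only a short call about four weeks later remains. Section 7.0 expects 10-15% dropout at each subsequent session.

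**The concern.** Two problems arise. They are alternatives and do not form a chain.

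**If the analysis sentence is followed literally**, anyone who finishes Session 2 and does not come back meets the primary outcome but not the analysed event. That is the dropout the protocol itself uses to define acceptability.

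**If post-session withdrawals are counted**, the opportunity is unequal by period. Session 2 is followed by another stimulation visit of 2-3 hours; Session 3 is followed only by the rest of that visit and a phone call. An analysis that treats the two sessions alike puts Session 3 exposures in the denominator with little chance of contributing a post-session event.

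A Bayes factor can support the null, so an omitted or attenuated difference can be read as evidence that tACS is as acceptable as sham.

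**Working it through.** **The plan's own figures (Section 7.0).** 30 enrolled with 30% overall dropout leaves 30 × 0.70 = 21, consistent with at least 20 completers. Two transitions at 10-15% lose 1 − 0.90² = 19.0% to 1 − 0.85² = 27.8%, leaving 24.3 to 21.7. The plan gives no figure for the withdrawal comparison.

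**People at stake.** Between Sessions 2 and 3 the plan's rates imply 30 × 0.90 × 0.10 = 2.7 to 30 × 0.85 × 0.15 = 3.8 dropouts, so about 3 or 4.

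**Effect on the Bayes factor.** Assumed, because the plan gives none: two independent binomials, uniform priors, and 15 stimulated per order. For x/n active and y/m sham,

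BF01 = (n+1)(m+1)·C(n,x)·C(m,y) / [(n+m+1)·C(n+m, x+y)].

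Take 4 withdrawals after an active Session 2 and 0 after sham. All 15 sham-first participants return for active, giving 30 active sessions. Of the active-first participants 11 return for sham, giving 26 sham sessions.

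- Randomised Session 2 groups, 4/15 v 0/15: 16 × 16 × 1365 / (31 × 27405) = 0.41.
- Sessions pooled, 4/30 v 0/26: 31 × 27 × 27405 / (57 × 367290) = 1.10.
- Event in the analysis sentence, 0/30 v 0/26: 31 × 27 / 57 = 14.7.

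A less one-sided split, 3 v 1, gives:

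- Randomised groups, 3/15 v 1/15: 16 × 16 × 455 × 15 / (31 × 27405) = 2.06.
- Pooled, 3/29 v 1/27: 30 × 28 × 3654 × 27 / (57 × 367290) = 3.96.
- Analysed event, 0/29 v 0/27: 30 × 28 / 57 = 14.7.

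The literal analysis returns about 14.7 whichever way these four dropouts fall, because it does not see them.

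**Attenuation if sessions were pooled.** Let T be the true withdrawal risk per exposure and D the part occurring during the session. Assume no post-session event is counted after Session 3. The expected pooled active rate is

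[15·T_A + 15(1 − T_S)·D_A] / [15 + 15(1 − T_S)],

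and sham is the mirror image. With assumed T_A = 20% and T_S = 10% (a 10-point difference), the denominators are 28.5 and 27:

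| Split of withdrawals | Active | Sham | Difference kept |
|---|---|---|---|
| All post-session (D = 0) | 3/28.5 = 10.5% | 1.5/27 = 5.6% | 5.0 points, 50% |
| Even by count (D = T/2) | 4.35/28.5 = 15.3% | 2.1/27 = 7.8% | 7.5 points, 75% |
| Even by risk (D_A = 1 − 0.80/0.90; D_S = 1 − 0.90/0.95) | 4.5/28.5 = 15.8% | 2.13/27 = 7.9% | 7.9 points, 79% |
| All during (D = T) | 5.7/28.5 = 20% | 2.7/27 = 10% | 10 points, 100% |

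If half the post-session risk persisted after Session 3, 75% would be kept even with every withdrawal post-session. When T_A = T_S the two expressions coincide, so with 1:1 order no false difference arises.

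**The case against.** The strongest reply is that the analysis sentence is loose shorthand. It directly follows a reference to dropout rate, so the authors may intend to count all withdrawals. That is plausible, but it does not rescue the plan: the window, attribution and denominator for the post-session part would still be missing, and the choice among them changes the answer.

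A reader might also infer more than the documents support:

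- *That the planned analysis is biased by pooling.* The plan never says sessions are pooled. Pooling is one reading among several.
- *That the mismatch causes dilution.* It cannot. A request to discontinue can occur in either stimulation session, so under that event post-session withdrawals are omitted, not diluted.
- *That withdrawal after Session 3 is impossible.* The Flanker task still follows stimulation there, and the call can be refused. Opportunity is unequal, not absent.
- *That a true difference is halved.* That is the limiting case.
- *That pooling always moves the Bayes factor toward no difference.* In simulation with the same priors, 20% v 10% all post-session, the chance that the Bayes factor for a difference falls below 1/3 rises from 27% (first stimulation session only) to 69% (pooled). With 30% v 5% all during the session, its median rises from 1.60 to 4.47. With 20% v 10% all during, it falls from 0.49 to 0.40 although nothing is diluted.

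It is also fair to say that a first-period comparison is weak. At an assumed 20% v 5%, all post-session, 15 v 15 gives a Bayes factor above 3 for a difference only about 10% of the time (pooled: 3%) and above 3 for no difference about 27% of the time (pooled: 57%). In a 30-person pilot this objection stands as a limit on what the remedy can show.

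**Conclusion.** The concern holds as a mismatch between a primary outcome and its analysis, together with undefined handling of post-session withdrawal. As written, the analysis omits an expected 3 or 4 between-session dropouts. In the 4 v 0 illustration this moves the Bayes factor for no difference from 0.41 to 14.7. The figure depends on the assumed uniform priors, 15 per order and a deliberately one-sided split; at 3 v 1 the shift is from 2.06 to 14.7.

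The attenuation is conditional on pooling, which is not stated. It ranges from nil to about half, with 20-25% at an even split, under true rates that the documents do not supply. The documents do not support saying that the trial's analysis is biased toward tACS, only that readings left open can favour the reassuring answer. The plan should be corrected before the withdrawal data are analysed.

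**What to change.** Use one definition of the withdrawal outcome in the synopsis, Section 2.0 and Section 7.0, and analyse two components:

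- **(a) Stimulation discontinued during the session**, compared over all active and sham sessions started.
- **(b) Withdrawal after the first stimulation session and before Session 3**, compared between the groups randomised to active or sham at Session 2, with everyone stimulated at Session 2 as denominator.

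State the Bayes factor model and prior for each component, including how (a) allows for two sessions per person. Report (b) with interval estimates beside the Bayes factor.

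The cost is wording; no new data are needed. The downside is that (b) gives up the within-person comparison and rests on about 15 v 15, fewer if some leave between randomisation and Session 2, so it will be imprecise.

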- 4) *Self-Rated Assessments*. Participants will fill out BDI, ASRM, and PSWQ questionnaires. Any additional questionnaires not completed at the previous visit may be completed at this time or given to the participants to complete at home.
- 5) EEG and brain stimulation. EEG procedures will be repeated from Session 1. CF (cross frequency)-tACS targeting theta-gamma PAC will be administered in accordance to Consultant [name]'s published protocol⁴, which has successfully enhanced theta-gamma PAC and cognitive control in non-psychiatric individuals. Participants will be fitted using a montage consisting of 9 electrodes placed over the left frontal scalp.

Soterix Medical High-Definition Transcranial Alternating Current Stimulation device (HD-tACS) will be used to deliver current to the electrodes to generate tACS resembling theta-gamma PAC^{4,10,11}. The impedance of each stimulation electrode will be kept below 10 k Ω . The stimulation waveform will consist of a theta component (5 Hz) delivered at 0.96 mA (1.92 mA peak-to-peak) delivered in a constant sine wave and a gamma component (50 Hz), 3.5 cycles of a sine wave delivered at 0.64 mA (1.28 mA peak-to-peak) superimposed on the theta component and centered on the peak of each cycle. For both tACS and sham conditions, the stimulation will slowly ramp up over the course of 12 s, then the task will begin soon after maximum stimulation output is reached. Stimulation will be maintained at a stable level until the task is complete and the stimulation will ramp down over 12 s. Actual parameters may be varied slightly, but not enough to affect the risk to the participants.

tACS Study (HUM00208557)

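### Primary outcome 6 (theta-gamma PAC) rests on rest EEG blocks that the session procedures do not describe and whose current status is not stated

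*Combined protocol and SAP*

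**What the plan says.** Section 2.0 gives primary outcome 6 as "Theta-gamma PAC (Kullback-Leibler Modulation Index) during the rest EEG blocks interleaved between stimulation blocks". Section 7.0 (Aim 2) analyses PAC in the rest blocks, comparing tACS with sham within subjects. It cuts rest data into 2 s epochs and task data into epochs from -400 to 1800 ms.

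Section 5.2 (Sessions 2 and 3, item 5) describes the delivery of stimulation: a 12 s ramp-up, a task that starts soon after full output, and then "Stimulation will be maintained at a stable level until the task is complete and the stimulation will ramp down over 12 s". Item 6 makes that task 640 trials in 8 blocks of 80. For the recording itself, item 5 says "EEG procedures will be repeated from Session 1", and in Session 1 the EEG accompanies the Go-NoGo and Flanker tasks. The only EEG that Section 5.2 places after stimulation is the Flanker recording (item 8). The design paragraph of Section 2.0 says "The second and third sessions will involve tACS brain stimulation (or placebo stimulation) during a computerized task and EEG recording".

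The waveform is a 5 Hz theta sine wave with "a gamma component (50 Hz), 3.5 cycles of a sine wave delivered at 0.64 mA", "superimposed on the theta component and centered on the peak of each cycle". Sham receives the genuine waveform at full strength for 12 s and is then ramped down. Under Section 4.2, the PI and the data analyst know the assignment.

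**The concern.** PAC is the only neural measure among the six primary outcomes, and Section 1.4 presents the study as proof of concept that tACS engages this neural target. The section that defines the outcome and the section that describes the sessions do not match. Section 2.0 needs stimulation that stops and restarts, with rest EEG in the gaps. Section 5.2 gives no gap and no rest recording.

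Two things are at stake. First, sessions run from Section 5.2 alone would not produce the data that define outcome 6. Second, if that were met by computing PAC from EEG recorded while current flows, the recording could contain the stimulator's own coupled waveform in the active session, and in sham only around its brief initial delivery. A tACS-sham difference in PAC could then reflect the device and not the brain.

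**Working it through.** The plan gives no figure for the rest blocks, so there is none to reproduce. The power statement in Section 7.0 does not bear on this point. The check sets the sections side by side and adds short arithmetic on the waveform.

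**1. Stimulation runs per session**

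| Source | Runs | Rest EEG blocks |
|---|---|---|
| Section 2.0, outcome 6 | at least 2 (something must lie between stimulation blocks) | at least 1, number not given |
| Section 5.2, items 5 and 6 | 1 (one ramp-up, one ramp-down, held until the task ends) | 0 mentioned |
| Section 7.0, Aim 2 | not stated | assumed to exist; 2 s epochs |

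If each of the 8 task blocks were meant as its own stimulation block (an assumption), there would be 8 runs and 8 - 1 = 7 gaps. Section 5.2 ties the end of stimulation to the end of the task, not of a block. The 2 s figure is the length of an analysis segment and not of a rest block.

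**2. Where EEG is recorded**

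- Session 1: during the Go-NoGo and Flanker tasks.
- Sessions 2 and 3: Session 1 procedures repeated, with Flanker EEG after stimulation.
- Section 5.4: the EEG and tACS rows carry the same footnote, the Go-NoGo task. This is supporting evidence only, because the table also omits the Flanker EEG.

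None of these is a rest recording.

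**3. What the waveform would do to PAC if recorded**

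- Gamma burst: 3.5 cycles / 50 Hz = 0.070 s = 70 ms.
- Theta cycle: 1 / 5 Hz = 0.200 s = 200 ms.
- Share of each cycle: 70 / 200 = 35%, centred on the theta peak.

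The signal is therefore theta-gamma coupled by construction. Its 5 Hz and 50 Hz components lie inside the 4-8 Hz and 30-60 Hz bands named in Section 1.3. They also lie inside the 0.1-100 Hz filter and the 2-60 Hz wavelet range of Section 7.0, which itself names no PAC bands.

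**4. Safeguards in Section 7.0**

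Independent component analysis (ICA) and a voltage threshold are listed as general steps. Neither is written for stimulation artifact, and the text does not say who rejects ICA components or by what rule. With Section 4.2, those choices can fall to someone who knows which session was active.

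**The case against.** The strongest reply is that the definition already protects the outcome. Sections 2.0 and 7.0 both confine PAC to rest blocks, placement between stimulation blocks implies that current is off, and rest data are epoched separately from task data. This stands. A reader might infer that the plan will compute PAC from EEG contaminated by stimulation; the documents do not support that, and no section says it.

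A second reply is that Section 5.2 never calls the stimulation unbroken. This also stands. A single run is the natural reading, but delivery block by block is not excluded.

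Third, the detail may lie elsewhere. The study schema was not readable in the copy reviewed, and Section 5.2 refers to a published protocol that may hold a block structure. Absence can therefore be claimed only for the readable text. A schema showing rest blocks would supply the missing detail, but Section 5.2 would still need to be brought into line with it. The allowance in Section 5.2 for slight variation in parameters does not create rest recordings.

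Fourth, a reader might infer that no rest EEG is being collected. Section 2.0 is part of the protocol too, so staff may well be recording it. The documents do not settle this.

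Last, the analyst's knowledge of assignment could be called a separate blinding matter. It belongs here to the extent that choosing segments and rejecting ICA components are the steps at which that knowledge could influence outcome 6.

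**Conclusion.** The plan contradicts itself on how the data for primary outcome 6 arise, and it leaves the rest blocks unspecified. This is an internal inconsistency, not a design choice that can be debated on its merits. Confidence in the textual mismatch is high.

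The consequences are conditional:

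- If Section 5.2 is followed as written, outcome 6 cannot be computed as defined.
- If current-on EEG were substituted, the 5 Hz/50 Hz waveform would be confounded with the active-sham contrast.
- If the rest blocks are recorded with current off, as Section 2.0 implies, that confound does not arise and the remaining defect is one of specification.

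No bias size is claimed, because the documents give nothing from which to derive one. The point affects one of the six primary outcomes, but it is the one that carries the target-engagement claim, so it should be fixed. The conclusion rests on reading Section 5.2 as a single run and on the readable text alone.

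**What to change.** 1. Reconcile Sections 2.0, 5.2 (Sessions 2 and 3, items 5 and 6), 5.4 and 7.0 on when current is on and when rest EEG is recorded. State the number, length, timing and current status of the rest blocks. No view is taken here on which stimulation schedule is right.
2. State in Section 7.0 that PAC is computed only from rest EEG recorded with no current flowing, with ramps excluded, and in the same time windows for active and sham.
3. Preprocess the EEG under coded session labels until ICA component rejection is locked, and state who rejects components and by what rule. Cut any current-on segments by time marker first, since a visible waveform would reveal the active session. Section 5.2 has the postdoctoral fellow or the PI program the randomization list; whichever of them does not process the EEG should hold the key. Record this in Section 4.2.

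**Cost.** If current-off rest blocks are already recorded, this takes a few sentences in Sections 2.0, 4.2, 5.2, 5.4 and 7.0 and a small label-coding step. If they are not, item 1 needs a procedural change or a redefined outcome 6, and the documents do not allow that cost to be sized. In both cases, EEG recorded with current on or during ramps is not used for PAC.
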